| SAFETY & COMPLIANCE | | | | | | |
| Study visit monitoring | Vital signs; Adverse events | | Х | | Х | Х |
| Treatment monitoring | Monitoring visits: Adverse events; vitals | | | Х | | |
| Treatment monitoring | Staff phone calls: Adverse events | | | | Day 2, 36, 43, 50 | |
| | Phone call reminder | | | Х | Х | Х |
| Medication compliance | Pill counts; self-report | | | X | Х | Х |
| | Review of smart caps logs (opening times/dates) | | | X | Х | X |
| Behavioral intervention | Brief motivational intervention (following NPU task) | | Х | | Х | On lapse |
| Acute craving (for study release) | Desire for Alcohol Scale (following NPU task; repeat as needed) | | Х | | Х | |
| OUTCOMES | | | | | | |
| Stress reactivity | Startle potentiation and self-report negative affect in NPU task | | Х | | Х | |
| | Perceived Stress Scale | | Past w eek | Past w eek | Past w eek | Past w eek |
| Alcohol use | Blood alcohol concentration (via breath test) | Х | Х | X | Х | Х |
| | TLFB (continuous abstinence, days drinking/w eek, drinks/day) | | Since last visit | Since last visit | Since last visit | Since last visit |
| Craving | Penn Alcohol Craving Scale | | Past w eek | Past w eek | Past w eek | Past w eek |

C4. Doxazosin Dosing Schedule

| TABLE 2 | TREATMENT DAY | DISPENSATION DAY (mg/capsule) | DAILY DOSE |
|-----------|---------------|-----------------------------------|------------|
| TREATMENT | 1 - 5 | Day 1: Study Visit 1 (1 mg) | 1 mg qd |
| | 6 - 9 | Day 6: Monitoring Visit 1 (2 mg) | 2 mg qd |
| | 10 - 13 | | 4 mg qd |
| | 14 - 17 | | 6 mg qd |
| | 18 - 28 | Day 18: Monitoring Visit 4 (4 mg) | 8 mg qd |
| | 29 - 56 | Day 29: Study Visit 2 (4 mg) | 8 mg qd |
| TAPER | 57 | Day 57: Study Visit 3 (6 x 1 mg) | 6 mg qd |
| | 58 | Day 58 (4 x 1 mg) | 4 mg qd |
| | 59 | Day 59 (2 x 1 mg) | 2 mg qd |
| | 60 | Day 60 (1 x 1 mg) | 1 mg qd |

All doxazosin and matched-placebo capsules will be prepared and blinded by the University of Iowa Pharmaceuticals, randomized by the UW Pharmaceutical Research Center and distributed through the UW CRU. Half the participants (N=80) will receive doxazosin and half (N=80) will receive a matched number of placebo pills daily for 8 weeks of

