treatment. The target therapeutic dose (8 mg doxazosin) will be achieved after an 18-day dose escalation schedule. Medication will be distributed across 6 visits. Participants will be provided 3-5 days of extra pills of their current dose at each distribution to provide flexibility in missed appointments; however, participants will not receive their next escalated dose until they attend an in-person visit. On study completion all participants will taper off doxazosin (or placebo) over 5 days using a protocol successfully employed by our consultant [name] in a recently completed smoking cessation trial. Participants who withdraw from the study will be tapered using the same protocol. There are no adverse effects with rapid cessation that may occur in other noradrenergic drugs (e.g., propranolol rebound hypertension)¹³¹.

C5. Medical Monitoring And Medication Compliance

[figure not shown]
Participants' safety will be evaluated by the study staff and medical staff via measurement of vital signs and self-report of medication side effects, adverse events, medication compliance and alcohol use at each of the three Study Visits (Day 1, 29, 57). Study staff will call participants on Day 2 to monitor (via self-report) adverse events and initial compliance with taking the first pill on Day 1. In addition, participants will attend four additional Medical Monitoring Visits at the UW Hospital the day of each dose escalation (Day 6, 10, 14, 18) for similar evaluation. As such, participants are evaluated in person prior to each dose escalation and at 4 weeks and 8 weeks into treatment.

Participants will complete safety check-ins weekly between Study Visit 2 and 3 (Day 36, 43, 50) to evaluate safety via self-report of medication side effects, adverse events, medication compliance, and alcohol use. These check-ins can occur via phone call or electronic survey according to participant preference. For participants who opt for electronic surveys, study staff will follow-up via phone if the participant reports side effects or problems or if the participant does not complete the survey. While we anticipate that subjects will tolerate study medication well, should participants experience adverse medication side effects, titration will be stopped at the highest tolerable dose. Maximum achieved dose will be included as a covariate in preliminary statistical models.

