On arrival at the Clinical Research Unit (CRU) in the University of Wisconsin Madison Hospital for the first study visit all participants will complete medical screening that will include review of medical history, review of medications, and screening clinical exam conducted by the provider. Medical staff will conduct clinical assessment to determine vital signs (including sitting and standing blood pressure and heart rate determinations). Twelve-lead ECG will be obtained in all participants. Laboratory evaluation will include chemistry panel comprehensive metabolic profile (Chem-12, assessing kidney and liver function, glucose level and electrolyte status), complete blood count (CBC), and thyroid stimulating hormone (TSH). All study visits will include blood alcohol concentration (BAC) breath-testing. A pregnancy test for women of childbearing potential will occur at all visits with the exception of Visit 3. This is not needed at Visit 3 as tapering the dose, which would be the response to a positive pregnancy test, will happen at this visit for all subjects.

Clinical assessment, clinical exam, and all other medical and medication screenings and monitoring will be conducted by medical staff. ECG interpretations will be confirmed by the study physician. All measures are reviewed by study staff to ensure that participants can safely use doxazosin and participate in the study. Specifically, participants will be excluded for FDA contraindications for doxazosin. All women of childbearing potential will be required to agree to use a study-approved method of birth control or abstinence to prevent pregnancy during the course of the study. Medically-related issues, if needed, will be discussed by the research staff and medical staff with a designated study physician who will be timely available via pager or cell phone.

Exclusion criteria are divided into three broad categories of Medical, Psychiatric/Behavioral, and Medications/Therapies. These criteria are all implemented to protect human subject safety, except where noted with an asterisk (*) denoting scientific/theoretical reasons. See Appendix C (Eligibility Criteria Checklist) for detailed description of eligibility criteria, assessment measures and assessors.

Medical exclusion

- Past or current coronary artery disease, cerebrovascular accident, unstable angina, history of myocardial infarction, history of congestive heart failure.

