- **5. Side effects from study medication (doxazosin):** The most common side effects associated with doxazosin are drop in blood pressure, dizziness, headache, drowsiness, lack of energy, weakness, palpitations, and nausea. Orthostatic hypotension and syncope (i.e., fainting) can occur in some individuals. Alpha1-NE antagonists have been associated with the so-called "first-dose phenomenon" whereby the possibility of fainting is higher after the first dose in 1% of the population. Syncope risk is increased with dehydration, especially when moving from lying or seated to standing. It is also possible that orthostatic hypotension and syncope could occur after the first dose following increase in dosage, or if therapy with the drug is interrupted.

One rare but serious side effect is priapism, which is a painful penile erection sustained for hours, that can lead to permanent impotence/erectile dysfunction if not promptly treated. The prescribing information for doxazosin suggests that this risk occurs less than once every several thousand people.

- **6. Confidentiality failure**: The questionnaires and psychophysiological measures to be used in the proposed research are generally of a benign nature. However, some self-report questionnaires yield sensitive information regarding alcohol use. If confidentiality is broken the information collecting in this study could have unanticipated or untoward consequences for the participant's reputation, employability, or legal status.
- **7. Alcohol craving following stressor exposure**: Participants are exposed to a stressor task (the NPU Task) during study visits 1 and 2. It is possible that this stressor could elicit mild, brief alcohol craving in study participants.

D2. Adequacy of Protection against Risks:

In this section, we outline the protections in place to reduce the risk associated with the risks identified in D1.

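### The only taper defined starts at 6 mg, with no entry point for active-arm participants at 1, 2 or 4 mg; read literally, it raises their dose before lowering it

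*Combined protocol and SAP*

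**What the plan says.** Table 2 in C4 (Doxazosin Dosing Schedule) sets out a titration through 1, 2, 4, 6 and 8 mg a day, followed by one taper. The first taper row reads "Day 57: Study Visit 3 (6 x 1 mg) | 6 mg qd". The next rows give 4, 2 and 1 mg on Days 58, 59 and 60. Each is a fixed count of 1 mg capsules.

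The text under the table applies this to completers, "On study completion all participants will taper off doxazosin (or placebo) over 5 days", and then to early leavers: "Participants who withdraw from the study will be tapered using the same protocol". Neither sentence refers to the dose being taken at the time.

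Other sections foresee people below 6 mg:

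- C5 says that, if side effects occur, "titration will be stopped at the highest tolerable dose".
- D2, item 5, allows a slower titration or a smaller final dose if side effects require it, and withdraws participants with significant side effects. D5 discontinues those with severe side effects. None of these is tied to a stage of treatment.
- D1 explains why no pregnancy test is needed at Study Visit 3: "tapering the dose, which would be the response to a positive pregnancy test, will happen at this visit for all subjects". So a positive test at an earlier visit also leads to tapering.

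On the effect of raising the dose, D1 (Potential Risks, item 5) warns: "It is also possible that orthostatic hypotension and syncope could occur after the first dose following increase in dosage".

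**The concern.** A taper that opens at 6 mg is a reduction only for someone taking more than 6 mg. For someone taking 1, 2 or 4 mg of doxazosin, the same capsule counts start with an increase. Some of these participants would be stopping because they did not tolerate the drug, and the protocol itself names hypotension and syncope as possible after an increase.

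What is at stake is safety and clarity of instruction. The efficacy analysis is not affected. Supply is part of the same gap: Table 2 ties taper capsules to Study Visit 3 on Day 57, and no taper dispensing is described for anyone who stops earlier.

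**Working it through.** **Inputs, all from Table 2.** Scheduled doses: 1 mg on Days 1–5, 2 mg on Days 6–9, 4 mg on Days 10–13, 6 mg on Days 14–17, 8 mg on Days 18–56. Taper: 6, 4, 2 and 1 mg on Days 57–60.

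**Reproducing the plan's figures.** Capsules × 1 mg: 6 × 1 = 6, 4 × 1 = 4, 2 × 1 = 2, 1 × 1 = 1 mg. The stated taper doses are reproduced.

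**Comparison with the current dose.** Change = first taper dose − current dose.

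| Current dose | Change on first taper day | Taper days above current dose |
|---|---|---|
| 1 mg | 6 − 1 = +5 mg | 3 of 4 (6, 4, 2 mg) |
| 2 mg | 6 − 2 = +4 mg | 2 of 4 (6, 4 mg) |
| 4 mg | 6 − 4 = +2 mg | 1 of 4 (6 mg) |
| 6 mg | 6 − 6 = 0 | 0 of 4 |
| 8 mg | 6 − 8 = −2 mg | 0 of 4 |

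Placebo participants have no rise.

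**Compared with the titration.** Going from 1 to 6 mg covers three scheduled steps, which the titration spreads from Day 5 to Day 14 (9 days) with visits on Days 6, 10 and 14. From 2 to 6 mg covers two steps, Day 9 to Day 14 (5 days). From 4 to 6 mg is one ordinary step.

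**When participants are below 6 mg.** By schedule this is Days 1–13, or 13/56 = 23% of treatment days, and longer for anyone held there. Table 1 places pregnancy tests at the monitoring visits (Days 6, 10, 14, 18) and at Study Visit 2 (Day 29). A participant on schedule arrives on Days 6, 10 and 14 having taken 1, 2 and 4 mg, so three of these five tests fall where the written taper starts above the current dose.

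**How many people (illustration only).** The Timeline section expects 85% of those completing the first visit to finish the study. With 80 per arm, 0.15 × 80 = 12 active-arm participants would stop early, assuming equal loss in both arms. If stopping is uniform over the 56 days, 12 × 13/56 = 2.8 stop on Days 1–13; if it is twice as concentrated early, 5.6. Completers held at a low dose would add to this, and people lost to contact, who receive no taper, would reduce it. The documents give no figure for either.

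**The rules side by side.**

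- *Held at 1, 2 or 4 mg for side effects, then completes.* C4 includes this person among all participants who taper, so Table 2 gives 6 mg on Day 57. C5 has already fixed a lower dose as the most they tolerate. Read literally, the two conflict.
- *Withdrawn for side effects at 1, 2 or 4 mg.* The same conflict arises through the withdrawal sentence in C4.
- *Stops at 1, 2 or 4 mg for another reason, such as a positive pregnancy test.* The C5 tolerability rule does not apply, so it is not breached. The first taper dose is still an increase.

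No section states where a participant below 6 mg enters the taper.

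**The case against.** The strongest reply is that tapering means reducing. Nobody would read a move from 1 to 6 mg as a taper, and the Table 2 rows follow directly on 8 mg, so they describe the ordinary completer. On that reading the plan omits a detail, and a descending entry would satisfy both C4 and C5. Safeguards also exist. The spare pills under C4 are of the current dose only. After Study Visit 1 a participant holds about 5 + 3 to 5 = 8 to 10 one-milligram capsules, whereas the full taper needs 6 + 4 + 2 + 1 = 13, so staff would have to dispense more. D2 gives the study physician a role in handling adverse events. C4 also takes the taper from a consultant's earlier trial, whose protocol may contain entry points that cannot be seen here.

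Much of this stands: a literal rise is unlikely. But the text uses fixed capsule counts and applies the same protocol to everyone who leaves. Intent and oversight make up for that wording without correcting it.

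Three stronger readings are tempting and are not supported:

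- *Every active participant below 6 mg would exceed a dose cap.* The C5 rule concerns only those limited by side effects.
- *The taper breaches the in-person rules.* C4 says "participants will not receive their next escalated dose until they attend an in-person visit" and C5 says "participants are evaluated in person prior to each dose escalation", but both, like the driving caution in D2, are written for the titration.
- *About 23% of participants are exposed.* That figure is a share of scheduled days and says nothing direct about people.

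**Conclusion.** The point holds and should be fixed. The written rule, followed literally, raises the dose by 5, 4 or 2 mg for active-arm participants at 1, 2 or 4 mg, and this sits against the protocol's own warning about dose increases. It directly contradicts the C5 tolerability rule only for participants held or withdrawn because of side effects. There is no rise at 6 or 8 mg or on placebo.

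The conclusion rests on Table 2 as printed and on the absence of an entry point anywhere in the documents; it does not assume that staff would apply the rule literally. A reader might infer that participants will in fact be given an increase. The documents do not support that, given the word taper and the physician's role. The number affected is not stated and is probably small. The blind is not the problem, since the Pharmaceutical Research Center maintains it (C3) and can break it when care requires (D2).

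**What to change.** Reconcile the Table 2 taper rows and the C4 text with C5, D1 (pregnancy), D2 item 5 and D5. The taper instruction and its blinded dispensing should be stated for participants whose current dose is below the first taper dose. This should cover those held at a lower dose, those withdrawn for side effects, those with a positive pregnancy test, and anyone else who stops before Study Visit 3. The schedule is left to the sponsor and the study physician; none is proposed here.

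In the same edit, make the 5 days given in C4 agree with the four taper dosing days in Table 2. This may only be a counting convention and carries little weight.

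The cost is a short protocol clarification and a matching pharmacy instruction. No analysis changes.

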Study staff will then prepare the participant for the NPU task with the application of physiological sensors. Next participants receive a series of shocks of increasing intensity (7 mA maximum) to assess their subjective tolerance threshold as per standard procedures from our laboratory^{22,128}. Their subjective maximum tolerated shock from the screening visit is used during the NPU tasks at both Visit 1 and Visit 2 to minimize individual differences in subjective pain tolerance. Next participants complete the NPU task (see below). After the NPU task, participants will be randomly assigned to drug group (doxazosin vs. placebo; between-subjects) in a stratified blocked schedule by sex using urn randomization procedures^{129,130}. The randomization and double-blind will be implemented and maintained by the UW Pharmaceutical Research Center (see letter of support), which is located in the same building as the CRU. All participants are told that they will receive either doxazosin or placebo during the study, but neither the participants nor the research staff will be aware of the group they are randomized to receive. Participants who are off study and were consented under a previous protocol which promised unblinding will still be unblinded, via phone contact after their last visit.

Participants will take the first study medication dose at home that evening after Study Visit 1 (Treatment Day 1). Staff will call participants on Day 2 to confirm initial compliance and monitor any adverse events. Participants continue 8 weeks of treatment including an 18-day escalating dose schedule up to a therapeutic dose (8 mg) of doxazosin (or placebo; see Doxazosin Dosing Schedule below). Additionally, participants will attend four medical monitoring visits during the first month of treatment (see below).

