If the participant affirms that they drove themselves, we will offer to call a cab or a friend to drive them. If this offer is declined, we will suggest that they should stay in the CRU or ARC until their BAC registers below 0.03. This release criterion has been used for many years in our other UW research that involves alcohol administration to research participants. As such, it seems equally appropriate for release for an ineligible participant who has self-administered their own alcohol. By way of comparison, a BAC of 0.08 is considered per se evidence of impairment from alcohol and with a BAC of > 0.05 alcohol impairment can be considered a contributing factor when accident or injury occurs.

If the participant declines to stay and indicates they plan to drive themselves, we will tell the participant that we will call the campus police so that the participant can make a more informed decision about what course of action to take. If the participant continues to indicate they plan to drive, we will call the campus police if the participant is driving away and provide information about the possibility of an impaired driver in the vicinity. We will not reveal the participant's name to the police in order to protect their confidentiality.

Statistical Analysis:

Planned Data Analysis for Specific Aims

Analyses for quantitative and dichotomous dependent measures will be accomplished within either General or Generalized (binomial family with logit link function) Linear Models, respectively, using R¹⁴⁰. In the sections below, we briefly describe the primary factors in statistical models to evaluate each Specific Aim. All models will include number of days abstinent at Visit 1 as an interactive between-subjects regressor to evaluate if drug effects and outcomes are comparable across alcoholics who vary in their previous duration of abstinence (1-8 weeks) on study initiation, although this has not moderated the effects on NPU task in our preliminary studies. Numerous individual difference measures (e.g., sex, mood/anxiety disorder comorbidity, tobacco use, trait affect, alcohol dependence severity, other treatment) are available to add to these models as interactive between-subject regressors in secondary analyses to evaluate possible individual difference moderators of drug effects.

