Doxazosin in usual medical practice is used to treat high blood pressure and urinary retention associated with benign prostatic hyperplasia; these indications have been associated with certain practices for medication initiation and titration that are optimized for these conditions. In this study, doxazosin is used as an alcohol relapse prevention pharmacotherapy. In this context, the considerations for optimal dosing take into account the risk-benefit ration of a given dose and its titration protocol versus, potential benefits of doxazosin therapy. Research documents the overall safety and superior results of the titration protocols similar to the proposed one, when compared with a slower-titration protocol or placebo for relapse prevention (or improving outcomes) among individuals with substance use disorders (108,148, https://clinicaltrials.gov/ct2/show/NCT01730846). In addition, the risk of alcohol relapse is highest in the first 3 months after stopping drinking in alcohol dependent adults, suggesting that effective interventions, when implemented early in the recovery, have the best potential to prevent relapse. Therefore, both evidence and conceptual framework derived from a natural history of alcohol dependence suggest an increased benefit of the proposed, previously-tested titration schedule in alcohol dependent adults, compared to a slower titration, typical in hypertension or BPH. Although the potential benefit of the proposed titration schedule and dosing appears to outweigh the potential risks (side effects) in this clinical population, we propose additional safeguards (i.e., the dose titration protocol will be modified slower titration, lower final dose) if the participant experiences side effects requiring such a modification.

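### Does adjusting for maximum achieved dose, a variable fixed after randomisation, undermine the Aim 2 intention-to-treat test?

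*Combined protocol and SAP*

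**What the plan says.** C5 (Medical Monitoring And Medication Compliance) states that if side effects occur, "titration will be stopped at the highest tolerable dose", and then that "Maximum achieved dose will be included as a covariate in preliminary statistical models". The sentence names no outcome, aim, placebo coding or consequence of fitting these models.

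Other sections determine what achieved dose is:

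- C3 places randomisation after the Visit 1 NPU task, before any study medication is taken. It adds that "neither the participants nor the research staff will be aware of the group they are randomized to receive".
- C4 says the comparison arm "will receive a matched number of placebo pills daily", and that "participants will not receive their next escalated dose until they attend an in-person visit".
- D2 provides that after side effects "the dose titration protocol will be modified slower titration, lower final dose".

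The statistical section (Planned Data Analysis for Specific Aims) states: "All models will include number of days abstinent at Visit 1 as an interactive between-subjects regressor". Individual-difference measures such as sex, comorbidity and tobacco use "are available to add to these models as interactive between-subject regressors in secondary analyses". The AIM 2 paragraph specifies a generalized linear model for any heavy drinking with a regressor for Treatment, run as intention-to-treat, and judges the prediction on the Treatment effect. Achieved dose is not mentioned anywhere in that section.

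**The concern.** Achieved dose is a consequence of what happens after allocation. Side effects on doxazosin lower it, so it probably differs by arm. Someone who stops attending before Day 18 never reaches 8 mg, and if relapse leads people to stop attending, the outcome partly determines the covariate. Conditioning on such a variable gives up the protection of randomisation.

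The C5 sentence is worded as a commitment, and *preliminary* could be read two ways: exploratory, or a first step that decides whether dose stays in the final model. The placebo coding is also open. If placebo participants are given 0 mg, dose nearly duplicates Treatment, and the Treatment coefficient then describes being assigned to doxazosin at a dose of zero. If such a model fed the Aim 2 decision, either the power or the type I error of that test could be badly damaged.

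**Working it through.** **1. Is dose in the Aim 2 test?** Set side by side, the sections give this:

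| Section | Term | Where it applies |
|---|---|---|
| AIM 2 paragraph | Treatment | the test that judges Aim 2, intention-to-treat |
| Planned Data Analysis | days abstinent at Visit 1 | all models |
| Planned Data Analysis | individual-difference measures | secondary analyses |
| C5 | maximum achieved dose | preliminary models only |

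No section moves dose from the last row to the first, describes screening covariates by significance, or chooses the Aim 2 model from earlier fits. As written, the Aim 2 test is free of dose.

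For Aim 1 the test is Treatment x Condition, a contrast of within-person differences. A main effect of dose, constant within a person, cancels from it.

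**2. What if dose were added anyway?** The plan gives no figure to reproduce: it states 80 per arm but no alpha, event rate, effect size or stopping rate. The following are therefore assumptions: two-sided 5%; heavy drinking 50% vs 28%; stopping below 8 mg in 5% vs 5%, 10% vs 3% or 20% vs 5% (doxazosin vs placebo); and those who stop spread evenly over the lower levels of Table 2 (1, 2, 4, 6 mg).

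Unadjusted power, normal approximation: the pooled rate is 0.39, the null SE is √(2 × 0.39 × 0.61/80) = 0.0771, and the alternative SE is √((0.25 + 0.2016)/80) = 0.0751. Then z = (0.22 − 1.96 × 0.0771)/0.0751 = 0.92, so power is about 82%. The simulated range is 81-84%.

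**3. Collinearity of dose with Treatment.** Let m and v be the mean and variance of the level reached in an arm (subscript 1 for doxazosin, 0 for placebo). With 1:1 allocation:

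- Level recorded in both arms: VIF = 1 + (m₁ − m₀)²/[2(v₁ + v₀)]
- Placebo set to 0 mg: VIF = 1 + m₁²/(2v₁)

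Those who stop have mean level (1+2+4+6)/4 = 3.25 and mean square (1+4+16+36)/4 = 14.25. At 10% stopping, m = 0.9 × 8 + 0.1 × 3.25 = 7.525 and v = 0.9 × 64 + 0.1 × 14.25 − 7.525² = 2.40. At 20%, m = 7.05 and v = 4.35. At 5%, m = 7.7625 and v = 1.26.

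- Level coding, 20% vs 5%: 1 + 0.7125²/[2 × (4.35 + 1.26)] = 1.05. With equal stopping it is 1.00.
- 0 mg coding: 5% gives about 25.0, 10% gives 1 + 56.63/4.80 = 12.8, and 20% gives 6.7.

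**4. Simulated Aim 2 test** (4,000 trials per scenario, likelihood-ratio test of Treatment; *link* is the latent correlation between stopping titration and drinking):

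| Dose coding and use | Power, no link | Type I error, no link | Type I error, with link |
|---|---|---|---|
| Level in both arms, always adjusted | 81-82% | 5.0-5.4% | 4.3-8.9% (0.3-0.5) |
| Level in both arms, kept only if p < 0.05 | 82% | 4.8-5.2% | 4.2-8.6% (0.3-0.5) |
| Placebo = 0 mg, always adjusted | 13-19% | 6-9% | 23-25% (0.3) |
| Placebo = 0 mg, kept only if p < 0.05 | 81-82% | 8.6-12.0% | 24-26% (0.3) |

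With level coding and a link, the median log odds ratio under the null moves from about 0 to at most −0.20 (odds ratio e^−0.20 = 0.82), towards apparent benefit. Adding days abstinent and its interaction changes little: in the 20% vs 5% scenario with correlation 0.3, level-coding type I error is 7.3% against 6.2%.

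The 0 mg power figures also depend on the test. At 10% vs 3% the likelihood-ratio test gives 15.5% and the Wald test 0.6%.

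**5. Which coding fits the design?** The investigator stops titration without knowing the arm, and placebo capsules are matched. What can be recorded under the blind is the titration level, in both arms. That corresponds to the first two rows of the table.

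**The case for a change.** The strongest case for a change is that the plan does not close the door. C5 says dose will be included, not that it may be. The statistical section says it describes the primary factors only briefly, so silence about dose is not exclusion; days abstinent belongs in every model and yet is not repeated under AIM 2. Dose is not among the examples sent to secondary analyses. Table 2 states dose in mg of doxazosin, so 0 mg for placebo is conceivable. One sentence would settle all of this at almost no cost.

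Part of this stands. *Preliminary* is undefined and the placebo coding is unstated. The simulation also leaves out early dropout, the route by which relapse itself could lower the recorded maximum, so the level-coding figures do not cover every mechanism in the plan; C4 withholds escalation without a visit, and the Timeline expects 15% not to complete.

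But these points show only that a harmful reading is possible. Each needs dose to reach the Aim 2 decision, and a brief description that names Treatment, intention-to-treat and a single covariate for all models does not invite that. A clarifying sentence would mostly restate what the AIM 2 paragraph already implies.

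**Conclusion.** No change is needed. C5 leaves a detail open, but the test that decides Aim 2 is specified elsewhere and does not contain achieved dose. Followed as written, its size and power are untouched. The natural reading is that dose-adjusted fits are exploratory.

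If an analyst did add dose, with titration level in both arms, the cost would be small: power essentially unchanged, and type I error near 5% unless stopping titration and drinking are linked. The 8.9% upper end belongs to a range extending to an assumed correlation of 0.5. The severe results (power of 13-19%, type I error of 23-26%) are hypothetical: they require 0 mg coding and dose entering the decision, and the 23-26% also requires an assumed correlation of 0.3.

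All event rates, stopping rates and correlations are assumptions, and early dropout is not modelled. The conclusion rests mainly on the text of the statistical section and less on these figures.
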